Vital Signs ^{d)}	X	X	X	X	X	X	X	X
Electrocardiogram (ECG)		X		X		X		X
Transthoracic echocardiography (TTE)		X		X		X		X

- a) The date when all assessments for Visit 2 are completed is set as “0 w” and the time of visit from Visit 3 onward will be counted from the date.
- b) Reconfirmation of inclusion/exclusion criteria will be conducted before randomisation.
- c) All subjects will be allocated to one of the two groups (0.033 mg/kg/day group or 0.066 mg/kg/day group) before procedures at Visit 2.
- d) Vital signs are blood pressure (diastolic and systolic) and pulse, both sitting after 5 minutes of rest.
- e) Clinical laboratory tests are haematology, biochemistry, lipid and endocrinology.
- Haematology: red blood cell (RBC), white blood cell (WBC), haemoglobin, haematocrit, platelets, and leukocytes fraction (neutrophil leukocyte, lymphocyte, monocyte, eosinophil leukocyte, and basophilic leukocyte)
 - Biochemistry: aspartate aminotransferase/serum glutamino-oxaloacetic-transaminase (ASAT/SGOT), alanine aminotransferase/serum glutamino-pyruvic-transaminase (ALAT/SGPT), gamma-glutamyl transpeptidase (γ -GTP), alkaline phosphatase (ALP), total protein, blood urine nitrogen (BUN), creatinine, sodium (Na), potassium (K), chloride (Cl), calcium (Ca), and phosphorus (P)
 - Lipid: total cholesterol, low-density lipoprotein (LDL)-cholesterol, and high-density lipoprotein (HDL)-cholesterol
 - Endocrinology: thyroid-stimulating hormone (TSH), free thyroxine (FT₄), and free triiodothyronine (FT₃)
- f) Bone metabolism markers are bone-alkaline phosphatase (BAP) and osteocalcin.
- g) Blood coagulation test is the measurements of prothrombin time and partial thromboplastin time.
- h) Urinalysis is the measurements of protein, glucose, and occult blood.
- i) These data will be treated as baseline data.
- j) In case that a subject is withdrawn from the trial, all assessments for visit 20 should be taken as soon as possible.

3 Background information and rationale for the trial

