8.3 Concomitant medication

A **concomitant medication** is any medication, other than the trial products, which is taken during the trial period (including the screening period).

Details of any concomitant medication must be recorded at Visit 1 (screening visit). Any changes in concomitant medication must be recorded at each visit as they occur.

The information collected for each concomitant medication includes trade name or generic name, indication, start date and stop date or continuation.

If a change is due to an AE, then this must be recorded and reported according to section [12](#). If the change influences the subject's eligibility to continue in the trial, the monitor must be informed.

In case of systemic adrenocortical steroid, the information collected for each concomitant medication includes route of administration. If start date is more than one year ago before date of Visit 1, the date of one year ago before Visit 1 can be recorded on the concomitant medication form in the CRF.

Prohibited concomitant medication

Concomitant use of the following drugs, which may effect on growth acceleration, will be prohibited during the trial.

Thyroid hormone (except the replacement treatment), anti-thyroid hormone, androgen, oestrogen, progesterone, anabolic steroid, systemic adrenocortical steroid, derivative of gonadotropin releasing hormone, somatomedin C (IGF-1), and GH preparation except for the trial products.

A use of systemic adrenocortical steroids (hydrocortison \leq 20 mg/day) for less than 13 weeks may be allowed.

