8.5.2 Laboratory assessments for safety

For laboratory analysis of safety parameters, the volumes of blood sampling at each visit are as follows:

- At Visit 1 (screening), Visit 8, Visit 12, Visit 16 and Visit 20, 14.1 mL of blood will be drawn for each visit.
- At Visit 3, Visit 5, Visit 7, Visit 9, Visit 11, Visit 13, Visit 15, Visit 17 and Visit 19, 5.5 mL of blood will be drawn for each visit.
- At Visit 6, Visit 10, Visit 14 and Visit 18, 7.8 mL of blood will be drawn.

The laboratory analyses will be performed by a central laboratory unless otherwise specified. Descriptions of assay methods, laboratory supplies and procedures for obtaining samples, handling and storage of samples and information on who will perform the assessments, will be described in a trial-specific laboratory manual provided by a central laboratory.

Laboratory samples can be drawn at another day than on the day of the actual visit as long as it is within the visit window stated in the flow chart (section [2](#)). For some samples drawn during the trial it is necessary for subjects to visit in fasting state for the sensitivity of the analysis.

The samples will be coded in order to keep subject identity anonymous.

Laboratory printouts except IGF-I will be sent by the central laboratory to the investigator on an on-going basis. All laboratory printouts must be dated and signed by the investigator on the day of evaluation. If a result is outside the normal range, the investigator must judge whether the abnormality is clinically significant. If considered clinically significant the result must be reported as an AE according to section [12](#).

If any clinically significant abnormalities occur at Visit 1, this must be recorded on the medical history/concomitant illness form. In the case of any clinical significant worsening since Visit 1 the investigator must comment in the medical record and the change must be reported as an AE according to section [12](#).

Laboratory printouts of IGF-I will be sent by the central laboratory to the investigator after the database lock of the extension phase (hereinafter referred to as 2nd database lock) in this trial to maintain double-blind design in this trial. All the laboratory printouts of IGF-I must be dated and signed by the investigator on the day of evaluation.

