1.2 Scope of the statistical analysis plan

This Statistical Analysis Plan (SAP) is based on the statistical analyses of GHLIQUID-4020 as planned in the trial protocol.

Changes to the statistical methods proposed in this SAP and the reason for the change must be reported in the clinical trial report (CTR).

This SAP is based on the protocol version 2.0 (Dated 03 March 2016).

2 Statistical considerations

Analyses of all efficacy endpoints will be performed based on the full analysis set (FAS). The primary analysis of the primary endpoint will be repeated on the per protocol (PP) analysis set.

Safety endpoints will be summarised using the safety analysis set (SAS).

The impact of protocol deviations and outliers may be investigated further in sensitivity analyses if deemed relevant.

Missing values for endpoints other than OGTT, HbA_{1c} and bone age will be imputed using the last observation carried forward (LOCF) method.

All endpoints will be summarised descriptively at each visit by treatment using observed data. After 104 weeks of treatment, descriptive statistics will be presented based on both observed and LOCF imputed data. Endpoints that are analysed untransformed and endpoints that are not formally analysed are summarised by the arithmetic mean, standard deviation (SD), median, and minimum and maximum value. Endpoints that are analysed log-transformed are summarised by the geometric mean, coefficient of variation (CV), median, minimum and maximum value.

LOCF imputed data will be used as the basis for plotting data.

A formal statistical test will only be performed at 104 weeks. Presentation of results from a statistical analysis will include the estimated mean treatment effects (LSMeans). Estimated mean

treatment differences (or ratios) will be presented together with two-sided 95% confidence intervals and p values for all endpoints analysed statistically.

For endpoints measured over time mean values will be plotted to explore the trajectory over time. Data collected before randomisation will only be summarised descriptively.

Statistical analysis will be performed twice, at 104 weeks and at the end of trial including extension phase.

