 - HLT: Complications associated with device NEC, Overdoses NEC, Underdoses NEC
 - PTs: Contraindicated drug administered, Drug administered to patient of inappropriate age
- Hyperglycaemia and new-onset diabetes mellitus - pre-defined MedDRA search
 - SMQ code: 20000041, narrow scope
- Malignant tumours - pre-defined MedDRA search
 - SMQ code: 20000194, narrow scope
- Central nervous system vascular
 - HLGT: Central nervous system vascular disorders
- Convulsion - pre-defined MedDRA
 - SMQ code 20000079, narrow scope
- Hyperthyroidism
 - HLT Thyroid hyperfunction disorders (MedDRA HLT code 10043740)
- Nephrotic syndrome
 - HLT Glomerulonephritis and nephrotic syndrome (MedDRA HLT code 10018365)

IGF-I

IGF-I SDS will be derived using a reference range^{vi}.

The measurements and their change from baseline during 104 weeks of treatment will be summarised descriptively.

Change in IGF-I and IGF-I SDS from baseline to 104 weeks of treatment will be analysed based on the ANCOVA model with treatment as a fixed effect and baseline as a covariate. A 95% confidence interval of the treatment difference will be provided.

HbA_{1c}

The measurements of HbA_{1c} and its change from baseline to 104 weeks of treatment will be summarised descriptively.

Clinical laboratory tests

The measurements and their change from baseline during 104 weeks of treatment will be summarised descriptively.

Glucose tolerance based on the OGTT

The measurements of glucose and insulin will be summarised descriptively.

AUC of glucose and AUC of insulin will be calculated by the usual trapezoidal. Before calculation of AUC, missing data in each individual profile with at least one valid data at screening will be imputed by mean value at each time point for all available data from all subjects. For 52 and 104 weeks, missing data in each individual profile with at least one valid data will be imputed by mean value at each time point for all available data from each treatment.

Before statistical analysis, both of AUC at baseline and at 104 weeks will be logarithmically transformed. Change in log-transformed AUC of glucose and AUC of insulin from baseline to 104 weeks will be analysed based on the ANCOVA model with treatment as a fixed effect and log-transformed baseline as a covariate. A 95% confidence interval of the treatment ratio will be provided.

Bone age

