Change in bone age and bone age/chronological age from baseline to 104 weeks of treatment will be analysed based on ANCOVA model with treatment as a fixed effect and baseline as a covariate. A 95% confidence interval of the treatment difference will be provided. Yearly Δ bone age/ Δ chronological age will be summarised and graphically presented.

Vital signs (blood pressures and pulse)

The measurements and their change from baseline during 104 weeks of treatment will be summarised descriptively.

Urinalysis

The measurements and their change from baseline during 104 weeks of treatment will be summarised descriptively.

Blood coagulation

The measurements and their change from baseline during 104 weeks of treatment will be summarised descriptively.

ECCG

The measurements and their change from baseline during 104 weeks of treatment will be summarised descriptively.

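### The SAP plans no count or shift table of abnormal urinalysis or thyroid results by dose; such results are counted only if the investigator reports them as adverse events

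*SAP*

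**What the plan says.** Protocol 17.4.2 and SAP 2.4.2 list change in urinalysis and change in clinical laboratory tests as secondary safety endpoints. The protocol flow chart (footnote h) states: "Urinalysis is the measurements of protein, glucose, and occult blood". Footnote e places TSH, FT4 and FT3 among the clinical laboratory tests. Under Protocol 8.5.2.5 and 8.5.2.8 both are sampled at Visit 1, Visit 3 and Visits 5 to 20, which is 10 visits to week 104 and 18 to week 208.

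For each of the two groups of tests, SAP 2.4.2 plans one thing: "The measurements and their change from baseline during 104 weeks of treatment will be summarised descriptively". SAP section 2 fixes what that means: "All endpoints will be summarised descriptively at each visit by treatment using observed data", and "endpoints that are not formally analysed are summarised by the arithmetic mean, standard deviation (SD), median, and minimum and maximum value". At week 104 the same statistics are also shown with missing values carried forward. SAP 2.4.3 repeats the approach at week 208.

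SAP 2.4.2 also adds adverse event tables built on MedDRA searches, including hyperglycaemia and new-onset diabetes, hyperthyroidism, and glomerulonephritis and nephrotic syndrome. The link from a laboratory value to those tables is in Protocol 8.5.2: "If a result is outside the normal range, the investigator must judge whether the abnormality is clinically significant". A result judged significant is then reported as an adverse event.

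**The concern.** The purpose of the trial is to compare two doses, and the SAP treats certain renal, thyroid and glycaemic harms as important enough for dedicated event tables. For the laboratory measures closest to those harms, a reader would want to know how many children in each dose group moved from a normal to an abnormal result. Neither SAP section 2 nor Protocol section 17 plans that number: there is no shift table, no out-of-range rule and no count with percentage for urinalysis or thyroid tests.

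Two things are at stake. First, a difference between doses in mild or moderate abnormalities, below the level at which an investigator reports an event, could go untabulated although the data are in hand. Second, if the urine results are graded or positive/negative, a mean and a mean change do not describe them properly, and the SAP states no alternative for categorical results.

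**Working it through.** **Number per arm.** Protocol 17.1 gives 21 per group for 80% power (difference 0.45, SD 0.5, two-sided 5%). The exact t-test calculation gives 20.4, rounded up to 21, so this reproduces. Allowing for 10% withdrawal, 21 / 0.90 = 23.3, rounded up to 24. The point does not depend on the power calculation; only the 24 per arm is used below.

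**Do the five statistics determine the count?** Assume a urine measure scored 0 to 4 (an assumption, since the scale is not stated), 24 children per arm, and all children negative at baseline. The change from baseline then equals the value itself.

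| | Arm A | Arm B |
|---|---|---|
| Grades | one 4, six 2s, 17 zeros | two 4s, eight 1s, 14 zeros |
| Sum | 4 + 12 = 16 | 8 + 8 = 16 |
| Sum of squares | 16 + 24 = 40 | 32 + 8 = 40 |
| Mean | 16/24 = 0.67 | 16/24 = 0.67 |
| SD | √[(40 − 16²/24)/23] = 1.13 | same, 1.13 |
| Median | 0 | 0 |
| Minimum, maximum | 0, 4 | 0, 4 |
| Children positive | 7 | 10 |

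The planned table would be identical for the two arms, for the value and for its change, although the counts differ by three. With fewer positives the same happens: {4, 3, 3} plus 21 zeros and {4, 4, 1, 1} plus 20 zeros both have sum 10 and sum of squares 34, with 3 and 4 children positive. The statistics therefore do not fix the count.

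**What a mean and an extreme show for thyroid tests.** Suppose 2 of 24 children lose 40% of FT4 and the rest do not change, with similar baselines. The arm mean moves by 2 × 40% / 24 = 3.3%. The minimum change would show the fall, but not whether one child or several had it. The summaries are also made visit by visit, so extremes at different visits cannot be traced to the same or different children, and no baseline-to-worst movement is shown.

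**Which results are counted elsewhere?** Three provisions, taken in order:
- Protocol 8.5.2: an out-of-range result is judged by the investigator, and becomes an adverse event if considered clinically significant.
- Protocol 12.1: a laboratory adverse event must point to disease or organ damage and be severe enough to need active management, which can include further tests or closer follow-up.
- SAP 2.4.2: treatment-emergent events are tabulated as subjects, percentages, events and rates.

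Results meeting that threshold are counted by dose. An abnormal result below it is not; it can show only as part of a visit's minimum or maximum.

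**Precision if counts were shown (exact 95% intervals, n = 24).** 0/24: 0 to 14.2%. 3/24 (12.5%): 2.7 to 32.4%. 5/24 (20.8%): 7.1 to 42.2%.

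**The case against.** A reader might infer that children with abnormal results are never counted by dose, or that only means are reported. The documents do not support either. Median, SD, minimum and maximum are planned at each visit, so an extreme value would be visible. Results judged clinically significant are counted per child as adverse events. The threshold is not especially high, since closer follow-up qualifies as active management, and investigators are blinded to dose, so their judgement lowers sensitivity without being made in knowledge of the arm. All of this stands, and it narrows the gap to abnormal results below the reporting threshold.

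A reader might also think that hyperglycaemia is poorly measured. It is not: HbA1c, OGTT glucose and insulin, and an ANCOVA of log AUC are planned, so urine glucose is a minor part of that evidence.

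A third tempting reading is that the thyroid event search is deficient because it covers overactivity only while Protocol 8.3 permits thyroid replacement. That does not follow. A hypothyroid event would appear in the general adverse event tables, FT4 and its change are summarised, and changes in concomitant medication are recorded at each visit.

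Two further objections stand in part. If urine protein and glucose are reported as quantities, the planned statistics are valid for them, and what is missing is the counts. And with 24 per arm, counts would be descriptive: 0 versus 4 children gives a Fisher p of 0.11, and 0 versus 5 gives 0.0496. Neither objection removes the reason to show the counts.

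**Conclusion.** The point holds in limited form. The plan contradicts nothing in the documents, but its stated rule is the only planned summary of urinalysis and thyroid values, and it does not yield the number of children with abnormal results in each dose group. It is also ill suited to urine results if they are graded or positive/negative. Abnormal results are counted by dose only through adverse event reporting. The gap is clearest for urine protein, occult blood, TSH, FT4 and FT3.

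The size cannot be stated as a rate, because the documents give no frequency of abnormal results. The 7-versus-10 example rests on an assumed 0 to 4 scale and invented grades; it shows only that the count is not recoverable. The importance is low: this is an inexpensive improvement to safety reporting, and it does not affect the primary analysis.

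**What to change.** In SAP 2.4.2:
- Urinalysis: state the result scale. If results are graded or positive/negative, replace the mean and SD summary with the number and percentage of children in each category, by visit and arm. In either case, add a shift table from baseline to the worst post-baseline result for protein, glucose and occult blood.
- TSH, FT4 and FT3: keep the present summary and add low/normal/high shift tables, from baseline to the lowest and to the highest post-baseline value, against the central laboratory's reference ranges.
- Use observed data, at weeks 104 and 208, in the safety analysis set.

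The cost is SAP wording and a few descriptive tables, with no new tests. Protocol 8.5.2 provides for electronic transfer of laboratory data to the sponsor and presupposes normal ranges, but it does not say that the ranges are part of the transfer, so this must be confirmed. The intervals will be wide, and a worst-value table also picks up passing abnormalities, so the tables should be labelled descriptive.

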2.1 Sample size calculation

Sample size calculations are described in the protocol section 17.1 and will not further be described here.

2.2 Definition of analysis sets

The following analysis sets are defined in accordance with the ICH-E9 guidance¹:

- Full analysis set (FAS): includes all randomised subjects. In exceptional cases subjects from the FAS may be eliminated. In such cases the elimination will be justified and documented. The statistical evaluation of the FAS will follow the intention-to-treat (ITT) principle and subjects will contribute to the evaluation “as randomised”.
- The PP analysis set will consist of all subjects in the full analysis set who fulfils the following criteria:
 - Have not violated any inclusion criteria
 - Have not fulfilled any exclusion criteria
 - Have a non-missing height at baseline
 - Have at least 52 weeks of treatment
 - Have at least one non-missing height after 52 weeks of treatment

Subjects in the PP set will contribute to the evaluation “as treated”.

- Safety analysis set: includes all subjects receiving at least one dose of investigational medicinal product (0.033 mg/kg/day and 0.066 mg/kg/day of NN-220). Subjects in the safety analysis set will contribute to the evaluation “as treated”.

Randomised subjects who are lost to follow up and where no information on exposure is available after randomisation will be handled as unexposed.

The decision to exclude any subject or observation from the statistical analysis is the joint responsibility of the study group members. The subjects or observations to be excluded and the reason for their exclusion will be documented and signed by all parties, prior to the database lock.

The subjects and observations excluded from analysis sets, and the reason for this, will be described in the clinical trial report.

2.3 Primary endpoint

The primary endpoint is change in height SDS from baseline to 104 weeks of treatment according to the Japanese reference dataⁱⁱ. A height SDS will be also calculated according to the Noonan syndrome reference data in Japaneseⁱⁱⁱ.

Statistical analysis

Since the primary objective of this trial is to evaluate the growth promoting effect of NN-220, the following hypothesis will be statistically tested; $H_0: \mu_1 = \mu_2$ vs. $H_1: \mu_1 \neq \mu_2$, where μ_i is the population mean, $i = 1, 2$ represents 0.033 mg/kg/day and 0.066 mg/kg/day, respectively. Primary analysis for the primary endpoint will be performed based on the ANCOVA model with treatment as a fixed effect and baseline height SDS as a covariate.

Sensitivity analysis

The same analysis as for the primary endpoint will be repeated on the PP analysis set.

All height SDS measurements at scheduled time points after randomisation will be analysed in a linear mixed model with treatment, time and interaction between treatment and time as fixed effects, baseline height SDS and interaction between baseline and time as a covariate and subject as a random effect. This approach assumes that data are missing at random according to the taxonomy defined by Rubin (1976)^{iv}. Treatment differences at 104 weeks will be estimated using this model.

Any marked difference concerning treatment differences between the sensitivity results and the result from the primary endpoint will be commented upon in the CTR.

Exploratory analysis

In order to investigate effects of sex, age at start of treatment and baseline height SDS on the primary endpoint, change in height SDS from baseline to 104 weeks of treatment will be analysed based on the ANCOVA model with treatment and sex as fixed effects and age at start of treatment and baseline height SDS as covariates. Parameter estimates for sex, age at start of treatment and baseline height SDS will be presented together with two-sided 95% CIs and p values.

Height SDS (Noonan syndrome reference data in Japanese)

In addition to height SDS according to the Japanese reference data, height SDS will be also calculated according to the Noonan syndrome reference data in Japanese. The change in height SDS (Noonan syndrome reference data in Japanese) from baseline to 104 weeks of treatment will be

analysed based on the ANCOVA model with treatment as a fixed effect and baseline height SDS (Noonan syndrome reference data in Japanese) as a covariate.

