Missing values for endpoints other than OGTT, HbA_{1c} and bone age will be imputed using the last observation carried forward (LOCF) method.

All endpoints will be summarised descriptively at each visit by treatment using observed data. After 104 weeks of treatment, descriptive statistics will be presented based on both observed and LOCF imputed data. Endpoints that are analysed untransformed and endpoints that are not formally analysed are summarised by the arithmetic mean, standard deviation (SD), median, and minimum and maximum value. Endpoints that are analysed log-transformed are summarised by the geometric mean, coefficient of variation (CV), median, minimum and maximum value.

LOCF imputed data will be used as the basis for plotting data.

A formal statistical test will only be performed at 104 weeks. Presentation of results from a statistical analysis will include the estimated mean treatment effects (LSMeans). Estimated mean treatment differences (or ratios) will be presented together with two-sided 95% confidence intervals and p values for all endpoints analysed statistically.

For endpoints measured over time mean values will be plotted to explore the trajectory over time. Data collected before randomisation will only be summarised descriptively.

Statistical analysis will be performed twice, at 104 weeks and at the end of trial including extension phase.

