17.1 Sample size calculation

The primary endpoint is change in height SDS from baseline to 104 weeks of treatment¹⁷. Since the primary objective of this trial is to evaluate the growth promoting effect of NN-220, the following hypothesis will be statistically tested; $H_0: \mu_1 = \mu_2$ vs. $H_1: \mu_1 \neq \mu_2$, where μ_i is the population mean, i

=1, 2 represents the 0.033 mg/kg/day and 0.066 mg/kg/day, respectively. Primary analysis for primary endpoint will be performed based on the analysis of covariance (ANCOVA) model with treatment as a fixed effect and baseline height SDS as a covariate.

The sample size is calculated using two sided two sample t-test for $\mu_1 = \mu_2$ with a 5% significance level.

According to Osio D., et al. (2005)⁷, the mean (SD) of change in height SDS of treatment with 0.033 mg/kg/day and 0.066 mg/kg/day from baseline was 0.8 (0.4) after 1 year and a further mean gain of 0.4 (0.7) was observed after 2 years (mean and SD for each treatment are not presented in the article). In the GHLiquid-1516 trial (Japanese subjects with short stature born small for gestational age), mean difference of height SDS between 0.033 mg/kg/day and 0.067 mg/kg/day was 0.6 at 104 weeks. The results of the sample size calculations with power 80% can be seen in [Table 17-1](#) for different SDs and mean treatment differences that can be detected.

Table 17-1 Sample size per treatment group with power 80%

		Mean difference of 0.033 mg/kg/day and 0.066 mg/kg/day					
SD	0.35	0.40	0.45	0.50	0.55	0.60	
0.40	22	17	14	12	10	9	
0.45	27	21	17	14	12	10	
0.50	34	26	21	17	15	12	
0.55	40	31	25	21	17	15	
0.60	48	37	29	24	20	17	

With mean difference $\mu_2 - \mu_1 = 0.45$ and $SD = 0.5$, 21 subjects per treatment group give power 80%. In the GHLiquid-1516 trial, withdrawal rates were 6.1% and 5.9% for 0.033 mg/kg/day and 0.067 mg/kg/day, respectively. Assuming 10% of withdrawal rate from this result, sample size was determined as 24 per treatment group in order to ensure the power on PP analysis set. Thus, the sample size of 48 subjects in total is set, assuming exclusion of 6 subjects from PP analysis set.

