17.3 Primary endpoint

The primary endpoint is change in height SDS from baseline to 104 weeks of treatment¹⁷.

Statistical analysis

Since the primary objective of this trial is to evaluate the growth promoting effect of NN-220, the following hypothesis will be statistically tested; $H_0: \mu_1 = \mu_2$ vs. $H_1: \mu_1 \neq \mu_2$, where μ_i is the population mean, $i = 1, 2$ represents 0.033 mg/kg/day and 0.066 mg/kg/day, respectively. Primary analysis for the primary endpoint will be performed based on the ANCOVA model with treatment as a fixed effect and baseline height SDS as a covariate.

Sensitivity analysis

The same analysis as for the primary endpoint will be repeated on the PP analysis set.

All height SDS measurements at scheduled time points after randomisation will be analysed in a linear mixed model with treatment, time and interaction between treatment and time as fixed effects, baseline height SDS and interaction between baseline and time as a covariate and subject as a

random effect. This approach assumes that data are missing at random according to the taxonomy defined by Rubin (1976)²⁷. Treatment differences at 104 weeks will be estimated using this model.

Any marked difference concerning treatment differences between the sensitivity results and the result from the primary endpoint will be commented upon in the CTR.

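### The mixed-model sensitivity analysis of height SDS names only a subject random effect; read literally, its week-104 standard error is too small if the spread between children grows over time

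*SAP*

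**What the plan says.** Under its sensitivity analyses, SAP 2.3 states: "All height SDS measurements at scheduled time points after randomisation will be analysed in a linear mixed model". The fixed effects are treatment, time and their interaction, with baseline height SDS as a covariate. The specification ends with "interaction between baseline and time as a covariate and subject as a random effect". Protocol 17.3 gives the same model and adds: "Treatment differences at 104 weeks will be estimated using this model".

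Neither document names a residual covariance, a random slope, visit-specific variances or a degrees-of-freedom method. Neither says whether time is categorical. SAP section 3, which lists departures from the protocol, is silent on this model.

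Two other statements bear on the point:

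- Protocol 17 says that treatment differences "will be presented together with two-sided 95% confidence intervals and p values for all endpoints analysed statistically", so the SE of this model will be reported in some form. SAP section 2 limits inference in time: "A formal statistical test will only be performed at 104 weeks".
- SAP 2.3 states how the result will be used: "Any marked difference concerning treatment differences between the sensitivity results and the result from the primary endpoint will be commented upon in the CTR".

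**The concern.** A subject random effect with nothing else implies one variance for every visit and one correlation for every pair of visits. The model adjusts for baseline height SDS. Four weeks after baseline, children have had little time to diverge; by week 104 they have had two years. If the spread does grow, the pooled variance is smaller than the week-104 variance, and week 104 is the only visit at which the model is used for inference.

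This is the only planned model-based alternative to LOCF, because the other sensitivity analysis repeats the same ANCOVA on the per-protocol set. An analysis meant to test robustness could therefore look more precise than the data allow. Leaving the structure open also means that it could be settled after the treatment codes are opened to the sponsor, which Protocol 11.2 places after the first database lock.

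**Working it through.** **Inputs**

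- Visits: weeks 4, 8, 12, 26, 39, 52, 65, 78, 91 and 104 (Protocol Table 2-1). Week 0 is taken as baseline (assumption).
- SD 0.5 at 104 weeks and 24 per arm (Protocol 17.1).
- Growth of SD: not given. Protocol 17.1 cites a change that "was 0.8 (0.4) after 1 year and a further mean gain of 0.4 (0.7) was observed after 2 years", and notes that "mean and SD for each treatment are not presented in the article". It is unclear whether the 0.7 is the SD of the second-year gain or of the cumulative change. Neither figure is a baseline-adjusted SD by visit.

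**The plan's own figure.** The documents give no SE for the mixed model. Their sample size does reproduce: difference 0.45, SD 0.5, two-sided 5% t-test gives 21 per group (power 81.2%), and 21/0.9 = 23.3, rounded up to 24. All 30 cells of Table 17-1 also reproduce.

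**Correct SE at week 104.** 0.5 × √(2/24) = 0.144, a 95% half-width of 0.29.

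**SE under the literal model.** With complete data, categorical time and baseline-by-time, the week-104 estimate equals the ANCOVA estimate. REML estimates the single total variance as the mean of the ten visit variances. Hence

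literal SE / correct SE = √(mean of SD²ₜ over the ten visits / SD²₁₀₄).

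Two worked cases:

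- Variance proportional to time: mean of t/104 = (479/104)/10 = 0.4606; √0.4606 = 0.679; SE = 0.144 × 0.679 = 0.098.
- SD proportional to time: mean of (t/104)² = 3.1926/10 = 0.3193; √0.3193 = 0.565; SE = 0.144 × 0.565 = 0.082.

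**All cases.** Type I error comes from 20,000 simulated null trials per case: 24 per arm, baseline covariate, REML random intercept, Satterthwaite degrees of freedom, serial correlation 0.95 / 0.85 per 13 weeks.

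| SD over time, ending at 0.5 | SE ratio | SE shortfall | Mean 95% half-width | Type I error (%) |
|---|---|---|---|---|
| Constant | 1.000 | 0% | 0.29 | 4.7 / 5.0 |
| Linear from 0.45 | 0.947 | 5% | 0.27 | 6.3 / 6.2 |
| Linear from 0.40 | 0.895 | 11% | 0.26 | 8.1 / 8.1 |
| Linear from 0.35 | 0.844 | 16% | 0.24 | 9.7 / 9.5 |
| Linear from 0.30 | 0.795 | 20% | 0.23 | 12.0 / 11.8 |
| Power curve through 0.4 at week 52 | 0.750 | 25% | 0.22 | 14.3 / 14.0 |
| Straight lines 0 to 0.4 (week 52) to 0.5 | 0.682 | 32% | 0.20 | 18.4 / 18.4 |
| Square root of time | 0.679 | 32% | 0.20 | 18.1 / 18.5 |
| Proportional to time | 0.565 | 43% | 0.16 | 27.2 / 26.9 |

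ANCOVA on the same data stayed at 4.8–5.3%. The two curves through 0.4 join a published SD pooled over both doses to the planning SD. They are illustrations, not a trajectory found in the documents.

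**Direct fit.** The stated model was fitted by REML to 100 simulated trials in each of three cases. The SE ratio was 0.99 (constant), 0.69 (variance proportional to time) and 0.57 (SD essentially proportional to time). The week-104 estimate matched ANCOVA to rounding error in every fit.

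**The case against.** The strongest reply is that the text leaves something out; it does not state a wrong model. Nothing in it excludes an unstructured covariance in the program, and the shortfall needs two further steps: that silence means a random intercept only, and that spread grows. Both are fair descriptions. But someone who follows the sentence exactly fits the random intercept, and a reader cannot tell which model was intended.

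The size rests on assumed trajectories. SD proportional to time implies 0.5 × 4/104 = 0.019 at week 4, below a measurement SD of 0.05 (itself an assumption). That makes the extreme case unrealistic early on, but it hardly moves the result. Holding the week-104 variance at 0.25 and putting 0.05² = 0.0025 of it at every visit gives √((0.2475 × 0.3193 + 0.0025)/0.25) = 0.571, still a 43% shortfall. Nor is 43% a ceiling: SD growing as time to the power 1.5 gives about 50%. It stands that the range is only the span of the cases tried.

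The consequence is limited. No decision rule uses this p value, and the planned comparison of treatment differences still works with complete data. SDs by visit and the ANCOVA interval will also be in the report, so a careful reader might notice the mismatch. All of this stands; it limits the harm but does not correct the interval.

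**Conclusion.** The concern holds, as a point that should be fixed but is not critical. As written, the model understates the week-104 SE whenever baseline-adjusted spread grows between week 4 and week 104. Modest growth (SD 0.40 to 0.50) costs 11% of the SE and raises a nominal 5% test to about 8%; the steepest case in the table costs 43% and raises it to about 27%. With constant spread there is no harm.

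These figures assume complete data, categorical time, SD 0.5 at week 104 and 24 per arm. If time were entered as continuous, neither the formula nor the unchanged point estimate would apply. With missing visits, the covariance also affects the estimate under missing at random; that was not quantified. Confidence is medium because the documents give no SD by visit.

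The damage is confined to the interval and p value of this sensitivity analysis. The primary ANCOVA and the sample size are untouched.

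**What to change.** Replace the model sentence in SAP 2.3 with:

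> Height SDS at all scheduled post-randomisation visits up to week 104 will be analysed by REML with treatment, visit (categorical), treatment-by-visit, baseline height SDS and baseline-by-visit as fixed effects and an unstructured within-subject covariance, with Kenward-Roger degrees of freedom. If this does not converge, the first of these to converge is used: first-order ante-dependence; random intercept and slope.

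The essential element is a structure, fixed in advance, that lets variance differ by visit. With complete data, unstructured and ante-dependence both reproduce the week-104 ANCOVA SE.

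The cost is two sentences, and intervals that may be wider than under the literal model. Unstructured needs 10 × 11/2 = 55 covariance parameters from 48 children (42 expected to complete), so the fallback may be needed; ante-dependence needs 10 + 9 = 19. Random intercept and slope is only approximate: in the cases tried its week-104 SE ratio was 0.93–1.14 and its type I error 2.6–6.2%. That is why it comes last.

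The SAP should also say that the same structure and fallback order apply to the week-208 run. With 18 post-baseline visits, unstructured needs 18 × 19/2 = 171 parameters and ante-dependence 18 + 17 = 35, so the fallback is more likely there.
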